5.6 Age at Enrollment

Age will be calculated in years relative to the subject's carfilzomib study enrollment date and based on the following SAS programming statement:

```
AGE = FLOOR((INTCK('MONTH', DOB, CONDT)
              - (DAY(CONDT) < DAY(DOB))) / 12);
```

where DOB=date of birth; CONDT=consent DATE

6 INTERIM ANALYSIS and EARLY STOPPING GUIDELINES

No interim analysis is planned for this study.

7 STATISTICAL METHODS

7.1 General Considerations

All statistical analyses will be performed in SAS® version 9, or later (SAS Institute Inc., Cary, NC, USA).

Summary statistics will be provided for all endpoints involved. For continuous variables, the number of subjects with non-missing data (n), mean, standard deviation, median, minimum, and maximum will be presented. For discrete data, the frequencies and percentages will be provided. Unless otherwise indicated, percentages will be calculated based on the number of subjects with non-missing data as the denominator.

For the efficacy analyses, point estimates will be accompanied by a two-sided 95% confidence interval.

The efficacy analyses will be performed separately by disease cohort (MM or solid tumor). All other analyses will be presented by disease cohort and overall unless otherwise specified.

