4.2 Full Analysis Set Population

The Full Analysis Set (FAS) population will serve as the primary population for the analysis of the disease response data. The FAS population is a subset of all enrolled subjects, with subjects excluded for the following reasons:

- No post-baseline endpoint data subsequent to at least 1 dose of study treatment on the PX-171-010 protocol (applicable only to PX-171-008 subjects).
- Lack of baseline data for those analyses that require baseline data

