7.7 Efficacy Analyses

The efficacy analyses will be performed by disease cohort and will be based on investigator's assessment recorded on the CRF page.

All efficacy analyses will be based on the FAS population.

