The number and percentage of subjects with events, the number and percentage of subjects censored will be calculated for each disease cohort (MM, solid tumor) by regimen. The denominator for each regimen will be subjects who had the regimen.

Kaplan-Meier method will be used to estimate the distribution of PFS. The 25%, 50% and 75% KM quartiles will be provided along with a two-sided 95% confidence interval ([Klein and Moeschberger, 1997](#)).

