7.7.4 Additional Efficacy Analyses

7.7.4.1 Objective Response Rate (ORR)

Best overall response will be determined by the local investigator for regimens with the common baseline using the International Uniform Response Criteria ([Durie et al. 2006, with corrections](#)) (IMWG-URC) and the European Group for Blood and Marrow Transplant (EBMT) criteria ([Bladé et al. 1998](#)) for multiple myeloma subjects and RECIST criteria ([Therasse et al. 2000](#)) for solid tumor subjects.

Objective response rate (ORR) is defined according to disease cohort:

- MM - ORR is defined as proportion of subjects for whom the best overall response is stringent complete response (sCR), complete response (CR), very good partial response (VGPR), or partial response (PR).

- Solid Tumor – ORR is defined as the proportion of subjects for whom the best overall response is confirmed PR or confirmed CR.

Point estimates for ORR will be accompanied by 2-sided 95% confidence intervals ([Clopper CJ and Pearson, 1934](#)).

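### The ORR has no stated denominator and no rule for a missing best response, so reset-baseline regimens and PX-171-008 subjects can lose non-responders from the count

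*SAP*

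**What the plan says.** SAP 7.1 sets a general default: unless the SAP indicates something else, "percentages will be calculated based on the number of subjects with non-missing data as the denominator". SAP 7.7 adds that "All efficacy analyses will be based on the FAS population".

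SAP 7.7.4.1 defines the ORR by disease cohort. For multiple myeloma (MM), "ORR is defined as proportion of subjects for whom the best overall response is stringent complete response (sCR" and so on through CR, VGPR and PR. For solid tumours, "ORR is defined as the proportion of subjects for whom the best overall response is confirmed PR or confirmed CR". Neither definition names a denominator or says what happens to a subject with no evaluable best response. The same section has best response determined over regimens that share a baseline and attaches a Clopper-Pearson 95% interval to the ORR.

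Elsewhere the SAP does name denominators. For PFS event and censoring counts (7.7.2), "The denominator for each regimen will be subjects who had the regimen". For adverse events (7.6.1), it is subjects with at least one carfilzomib dose.

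SAP 4.2 and protocol 10.3.2 exclude subjects from the FAS for two reasons: "No post-baseline endpoint data subsequent to at least 1 dose of study treatment on the PX-171-010 protocol (applicable only to PX-171-008 subjects", and "Lack of baseline data for those analyses that require baseline data".

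**The concern.** A response rate normally counts every treated subject, and those whose response is never established count as non-responders. Here two rules can take such subjects out of the denominator.

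- The 7.1 default, if it governs the ORR, leaves out anyone whose best response is missing. SAP 5.5 and 7.7.2 reset the baseline when a new anti-cancer agent is added, and 7.7.2 also does so for a carfilzomib dose or frequency increase. SAP 5.5 uses a PX-171-010 baseline for subjects who enter after progression or other therapy. A subject on a new baseline starts with no best response, and has none until a later evaluable assessment.
- The first FAS exclusion removes PX-171-008 subjects, who have solid tumours, because of something observed only after dosing.

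At stake are the point estimate, the n reported with it, and the exact interval. Two programmers working from the same text could also produce two different ORRs.

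**Working it through.** **Nothing to reproduce.** The documents give no expected ORR, no missing rate and no power figure. Planned enrolment is about 100 across both cohorts (SAP 2.3), without a split. PX-171-008 was planned at 15 subjects (protocol 1.3). The responder counts, missing counts and cohort sizes below are assumptions.

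**Step 1: who can have a missing best response.**

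| Group | Applicable baseline (SAP 5.5) | Best response with no evaluable PX-171-010 assessment |
|---|---|---|
| No progression or other therapy at entry, not from PX-171-008 | Initial study | Can come from the parent study |
| Progression or other therapy at entry | PX-171-010 | None |
| Baseline reset during PX-171-010 | Time of the change | None on that baseline |
| From PX-171-008 | PX-171-010 screening | None; removed from the FAS |

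The last three groups are exposed.

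**Step 2: can it happen?** The first scheduled on-study assessment is Cycle 3 Day 1 (protocol 7.6), which is Day 2 × 28 + 1 = 57. Before that, a leaver depends on the end-of-study assessment (protocol 7.7). SAP 7.2 plans to tabulate reasons for having no final visit, so some such subjects are expected.

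**Step 3: direction.** Let N be the subjects who should count, R the responders and m those removed, none of whom has a response.

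- Kept as non-responders: ORR = R/N.
- Removed: ORR = R/(N−m).
- Ratio: N/(N−m), which is at least 1. The ORR stays the same only if R = 0 or m = 0.

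**Step 4: size with N = 100, assumed ORR 25% or 50%.**

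| Removed | Factor | ORR 25% becomes | ORR 50% becomes |
|---|---|---|---|
| 5% | 100/95 = 1.05 | 25/95 = 26.3% | 50/95 = 52.6% |
| 10% | 100/90 = 1.11 | 25/90 = 27.8% | 50/90 = 55.6% |
| 20% | 100/80 = 1.25 | 25/80 = 31.25% | 50/80 = 62.5% |

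The factor depends only on the proportion removed, so it applies equally to a smaller regimen group.

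**Step 5: a mixed cohort.** Assume 85 MM subjects and 42 responders, with 10 subjects unassessed in PX-171-010. Only those of the 10 on a reset baseline are missing; the others keep a parent-study best response. Clopper-Pearson limits are the 0.025 quantile of Beta(x, n−x+1) and the 0.975 quantile of Beta(x+1, n−x).

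| Of the 10, on a reset baseline | ORR under the default (95% CI) |
|---|---|
| 0 | 42/85 = 49.4% (38.4–60.5) |
| 2 | 42/83 = 50.6% (39.4–61.8) |
| 5 | 42/80 = 52.5% (41.0–63.8) |
| 10 | 42/75 = 56.0% (44.1–67.5) |

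**Step 6: PX-171-008.** Assume all 15 planned subjects roll over and 3 respond.

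- All kept: 3/15 = 20.0% (4.3–48.1).
- Two removed: 3/13 = 23.1% (5.0–53.8).
- Five removed: 3/10 = 30.0% (6.7–65.2).

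No ORR is planned for this subset alone. Other solid-tumour subjects would dilute the effect on the cohort ORR.

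**The case against.** **The FAS sentence may already settle the denominator.** If all efficacy analyses rest on the FAS and the ORR is a proportion of subjects, that can be read as a proportion of the whole FAS. The PFS contrast is also imperfect, because the TTP section gives no denominator sentence either. This reading is possible. But naming a population does not say how a missing value counts within it. SAP 7.3 and 7.5 also name a population, and if that alone displaced the 7.1 default, the default would rarely apply. The ambiguity stands.

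**Most subjects may not be exposed.** A reader might infer that everyone without an on-study assessment drops out. The documents do not support that: subjects who keep the initial-study baseline can carry a parent-study best response. Nor would the direction be fixed if they were dropped. Removing 10 of the 85 above, with 5 or 7 parent-study responders among them, gives 37/75 = 49.3% or 35/75 = 46.7%, against 49.4%. For subjects from other parent studies, the FAS rule also retains those without on-study data. This objection stands and limits the point to the groups identified.

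**The PX-171-008 restriction has a basis.** That study had no prior efficacy assessments (protocol 7.8), and protocol 10.4.2 notes that response in these subjects may first appear in PX-171-010. That explains why they can lack data. It does not justify leaving treated subjects out of a response rate.

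**Early progressors should be captured.** Protocol 7.7 requires a disease assessment within 30 days of the last dose and before new therapy, so many will have a recorded progression and will count. A reader might assume that the missing subjects are mostly early failures; the documents do not show this. The direction in Step 3 does not depend on it.

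**Conclusion.** The point holds in limited form. Followed as written, the 7.1 default removes reset-baseline subjects without a later evaluable assessment from that regimen's ORR, and the FAS definition removes PX-171-008 subjects without post-baseline data. In both cases the ORR can only stay the same or rise, and the n behind its exact interval shrinks. The 5% to 20% removal rates are illustrative; the actual size cannot be derived from the documents. For reset-baseline subjects the conclusion also assumes that the FAS sentence does not override the default.

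A reader might go further and say that the one-study exclusion makes the solid-tumour and MM results non-comparable. The documents do not support that as a harm: efficacy is analysed separately by cohort (SAP 7.1), and no prespecified hypothesis is tested (protocol 10.1).

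The ORR is an additional analysis, not a listed primary or secondary endpoint. This should be fixed, but it does not undermine the study's main results.

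**What to change.** In SAP 7.7.4.1:

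- State that the ORR denominator is all treated subjects in the disease cohort who had the regimen, or the regimens sharing the baseline, including PX-171-008 subjects without post-baseline data.
- Count a missing or not-evaluable best response as non-response, and report the number of such subjects beside each ORR.
- State that the PX-171-008-only post-baseline exclusion does not apply to the ORR, and document this as a change from protocol 10.3.2. SAP section 1 already provides for recording such changes.
- Say how treated subjects without baseline data are handled, and give their number. Lifting the PX-171-008 exclusion alone would not bring all dosed subjects into the FAS, because the separate baseline-data exclusion would remain.

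The cost is a few sentences and a documented departure from the protocol, with no new data collection. The ORR becomes slightly less favourable. It would be conservative if some not-evaluable subjects had in fact responded, which is why their number should be shown.

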7.2 Subject Accountability

The number of subjects treated will be presented by disease cohort and overall.

The number and percent of subjects who terminated from the study and reasons for termination will be summarized. In addition, the number and percent of subjects who had a final visit and reasons for subjects who had no final visit will be presented.

7.3 Demographic and Baseline Characteristics

The following demographic and baseline characteristics will be summarized by both disease cohorts and overall unless otherwise indicated. Summary statistics will be tabulated based on the Safety population.

- Both Disease Cohorts
 - Age at the entry of PX-171-010: <65, \geq 65
 - Sex: female, male
 - Race: Caucasian, African American, Hispanic, Asian/pacific islander
 - Time since diagnosis (years) in PX-171-010
 - Clinical response assessment at entry of PX-171-010
- MM Cohort
 - Height (cm), weight (kg), body surface area (BSA), ECOG performance status, Neuropathy Grade (All data from time of entry in PX-171-010 except ECOG which is from the time of entry in initial study and entry in PX-171-010.)
 - Number of prior regimens (initial study)
 - Prior Bortezomib (initial study)
 - M-protein light chain isotype and heavy chain isotype (initial study and PX-171-010)
 - Measurable disease category (initial study)
 - Refractory status (initial study)

- Plasma cell involvement (<50%, >=50%) (initial study)
- Cytogenetics (initial study): normal/favorable, poor prognosis, unknown or not done
- FISH (initial study): normal/favorable, poor prognosis, unknown or not done
- Cytogenetics or FISH (initial study): normal/favorable, poor prognosis, unknown or not done
- Serum Beta-2 Microglobulin (mg/L) (initial study)
- Durie-Salmon Staging and Subclassification (initial study)
- Did the subject maintain the parent study's response until PX-171-010 enrollment?
- Did the subject meet IMWG criteria for disease progression until PX-171-010 enrollment?
- Solid Tumor Cohort
 - Tumor type (initial study)

7.4 Regimen Change

The number and percent of subjects who had regimen change during the study and reasons for regimen changes will be summarized as collected on regimen change case report form. In addition, type of regimen changes: carfilzomib dose level increased/decreased, dose frequency increased/decreased, or other anti-myeloma drugs added will be summarized .

7.5 Study Treatment Exposure and Compliance

The overall extent of study treatment exposure and dose information will be presented by disease cohort and overall in the Safety population using descriptive statistics:

- Study drug dose administered in initial study
- Duration of exposure, calculated as (last dose date in PX-171-010 – first dose date in the initial study + 1), for subjects with less than or equal to 60 days between the end of the initial study and enrollment in PX-171-010. For subjects with great than 60

days between the initial study and enrollment in PX-171-010, duration of exposure is the sum of the exposure during the initial study and the exposure during PX-171-010.

- Categorical summary of duration of exposure by number of weeks.
- Total number of treatment cycles (PX-171-010 only and initial study + PX-171-010) during which one or more doses of carfilzomib was administered per subject.
Categorical summary of the number of cycles received per subject (PX-171-010 only and initial study + PX-171-010)
- Overall treatment duration in weeks, calculated as weeks from first dose administration to last dose administration in PX-171-010, and treatment duration by regimen
- Number of weeks between last day of initial study and PX-171-010 enrollment
- Categorical summary of the number of weeks between last day of initial study and PX-171-010 enrollment
- Number of doses received per subject
- Average dose of carfilzomib (in mg/m²) administered across all cycles and average dose of carfilzomib (in mg/m², mg) by regimen
- Cumulative dose (mg) administered across cycles and cumulative dose (mg, mg/m²) by regimen

Summary of study drug administration will be summarized categorically as follows:

- First dose administered (mg/m²)
- Highest dose administered (mg/m²)
- Method of administration (IV bolus, IV infusion)
- Dose frequency
- Drug product administered (Lyophilized or not)
- Dose level reduced at least once due to AE
 - Number of dose level reduction due to and AE
 - AEs resulting in dose level reduction
- Dose level increased at least once

- Dose frequency reduction due to an AE
 - AEs resulting in dose frequency reduction
- Dose frequency increased at least once

Study drug administration data by cycle and cycle day and cumulative data (initial study and PX-171-010) will be listed for all subjects.

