PROCEDURES	
After screening, eligibility determination, and enrollment; subjects will receive carfilzomib according to the doses and schedules as summarized in the Study Treatment section of the Synopsis. Standard monitoring for hematologic and non-hematologic toxicity is outlined in Section 6.2. Subjects may continue carfilzomib treatment until disease progression and discussion with Onyx Medical Monitor, diagnosis of new malignancy, unacceptable toxicity, Investigator discretion, voluntary withdrawal, or commercial availability of carfilzomib.
 
Safety Measures. A complete blood count (CBC) including platelets and basic metabolic chemistry panel (eg, Chem 7 or 8) will be performed on Day 1 of each cycle. Other general safety monitoring (eg, physical examinations, imaging, specialty tests, etc.) shall be in accordance with institutional guidelines and as clinically indicated. These data will not be routinely collected.
 
Efficacy Measures. Tumor measurements and efficacy assessments will be in accordance with the methods employed in the subject's prior carfilzomib study. For subjects participating in a carfilzomib trial without prior tumor measurements and efficacy assessments (eg, PX-171-008), tumor assessments employing standard institutional methods will be conducted at the time of screening for the current study. Disease assessments (eg, extent of disease measurements and objective response category) will occur within 30 days prior to enrollment to determine eligibility, at least every 3 months throughout study participation, and at end of study. Refer to Appendix D–E for Response Criteria.
 
For subjects with multiple myeloma (MM) entering the extended study with a partial response (PR), minimal response (MR), or stable disease (SD); bone marrow biopsies for cytogenetic and fluorescence in situ hybridization (FISH) evaluation will be optional at screening. A bone marrow biopsy in these subjects will also be optional at end of study for cytogenetic and FISH evaluation if the reason for study

	
discontinuation is disease progression. For subjects with MM entering the extended study with stringent complete response (sCR), complete response (CR), or very good partial response (VGPR), a bone marrow biopsy for cytogenetic and FISH analyses will also be optional upon the establishment of disease progression.

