1 INTRODUCTION

1.1 CARFILZOMIB BACKGROUND

Carfilzomib (PR-171) is a tetrapeptide ketoepoxide-based selective inhibitor of the chymotrypsin-like activity of the 20S proteasome ([Demo 2005](#)). Carfilzomib is structurally and mechanistically different from the dipeptide boronic acid proteasome inhibitor bortezomib, which is currently approved for use in the treatment of patients with multiple myeloma ([Demo 2005](#), [Velcade 2008](#)). In preclinical studies, carfilzomib demonstrates potent anti-tumor activity in a variety of tumor models, including multiple myeloma (MM) ([Demo 2007](#), [Ivancsits 2006](#), [Kuhn 2007](#)).

1.2 PHASE 1 AND 2 EXPERIENCE WITH CARFILZOMIB IN HEMATOLOGIC MALIGNANCIES ([Carfilzomib IB 2010](#), [Stewart 2007](#), [Onyx Data on File](#))

Phase 1 clinical trials of carfilzomib have been conducted in subjects with hematological tumors, including MM, Waldenström's macroglobulinemia, non-Hodgkin's lymphoma (NHL), and Hodgkin's lymphoma. In a completed study (PX-171-001), carfilzomib dosing ranged from 1.2 mg/m² to 20 mg/m² daily for 5 consecutive days (QDx5) followed by 9 days' rest, in cycles repeated every 14 days. Dose-limiting toxicities (DLTs) associated with the highest dose (20 mg/m²) were Grade 4 thrombocytopenia and Grade 3 febrile neutropenia, and the maximum tolerated dose (MTD) was established at 15 mg/m².

In a completed Phase 1 Study PX-171-002, doses ranging from 1.2 mg/m² to 27 mg/m² are administered on consecutive day dosing (QDx2) twice weekly for 3 weeks, followed by 12 days rest, in cycles repeated every 28 days. DLTs observed at the highest dose (27 mg/m²) included thrombocytopenia and hypoxia, therefore the MTD was established at 20 mg/m². Observations of fever, chills, and rigors, and an elevated creatinine (Grade 2) observed on Day 2 of the 27 mg/m² cohort prior to dosing in this part of the study, led to the development of a stepped-up dosing regimen wherein carfilzomib administration is initiated with a dose at 20 mg/m² followed by escalation to 27 mg/m² after the first cycle.

The most common non-hematologic toxicity events reported from the Phase 1 studies are generally mild, low-grade nausea, diarrhea, dyspnea, headache, and constipation. A Grade 3

or 4–thrombocytopenia may occur in subjects with preexisting low platelets, with recovery occurring between treatments. Grade 3 or higher neutropenia and anemia have also been reported, but less frequently than thrombocytopenia.

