3.4 ESTIMATED STUDY DURATION

An individual subject is considered to have completed the study 30 days after the last administered dose of study drug in order to allow for safety follow up. Treatment with carfilzomib will continue until the earliest of the following:

- Confirmation of disease progression, and discussion with Medical Monitor
 - OR -
- Diagnosis of a new malignancy
 - OR -
- Unacceptable toxicity
 - OR -
- Investigator discretion
 - OR -
- Voluntary withdrawal
 - OR -
- Commercial availability of carfilzomib

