4 SUBJECT SELECTION

4.1 INCLUSION CRITERIA

Subjects must meet all of the following inclusion criteria to be eligible to enroll in this study:

1. Previous completion of a carfilzomib study within 90 days prior to first dose of study drug for Protocol PX-171-010.
2. Disease Assessments performed within 30 days prior to first dose of study drug for Protocol PX-171-010.

Ethical/Other

3. Written informed consent in accordance with federal, local, and institutional guidelines
4. Females of childbearing potential (FCBP)* must have a negative serum or urine pregnancy test, with a sensitivity of at least 50 mIU/mL, within 3 days prior to first dose of extended carfilzomib therapy study drug.

5. Subjects must agree to adhere to the study visit schedule and other study requirements and receive outpatient treatment and laboratory monitoring at the institution that administers the drug.

* Females of childbearing potential (FCBP): Defined as sexually mature females who have not undergone a hysterectomy or who have not been postmenopausal for at least 24 consecutive months (ie, who have had menses at some time in the preceding 24 consecutive months), or had a bilateral oophorectomy are considered to be females of childbearing potential.

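### SAP 7.5 counts the between-study gap as exposure at 60 days or less but not above, so a longer gap can give a shorter reported combined exposure

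*SAP*

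**What the plan says.** SAP 7.5 (Study Treatment Exposure and Compliance) summarizes a combined duration of exposure over the initial study and PX-171-010 in the Safety population, with a further summary in categories of weeks. The first rule is "calculated as (last dose date in PX-171-010 – first dose date in the initial study + 1", and it applies "for subjects with less than or equal to 60 days between the end of the initial study and enrollment in PX-171-010". Above 60 days, "duration of exposure is the sum of the exposure during the initial study and the exposure during PX-171-010". The section gives no reason for choosing 60 days and does not define the single-study exposure that enters the sum.

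The same section plans a gap summary, both continuous and categorical: "Number of weeks between last day of initial study and PX-171-010 enrollment". It also plans PX-171-010-only treatment duration, cycles, number of doses and cumulative dose, and it lists dosing data from both studies for every subject.

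Three other places bear on the rule:
- Protocol 4.1 requires "Previous completion of a carfilzomib study within 90 days prior to first dose of study drug for Protocol PX-171-010".
- The Protocol Synopsis (Procedures) puts enrollment before dosing: "After screening, eligibility determination, and enrollment; subjects will receive carfilzomib according to the doses and schedules".
- SAP 5.6 computes age at enrollment from the consent date. SAP 7.5 does not say whether that date also serves as enrollment for the 60-day rule.

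**The concern.** One variable has two meanings. Below the cut it includes time off drug between the studies, and above the cut it does not. Because eligibility extends to 90 days, subjects can fall on either side. Reported exposure then rises day by day with the gap up to the cut and falls abruptly beyond it, although nothing about the dosing has changed.

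The switch also uses a different interval from the one it includes or drops. The branch is chosen by days from study end to enrollment. The days at issue run from the last initial-study dose to the first PX-171-010 dose. The planned gap summary uses the first interval. It therefore shows roughly how many subjects fall under each rule, but not how many off-drug days were counted.

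The study's objective concerns long-term or continuing treatment, so combined duration is one of the figures a reader will use to judge how long-term the exposure was.

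**Working it through.** The plan states no figure on this point, so there is none to reproduce. The two rules can be written out and compared.

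**Notation**
- E1, E2: exposure within the initial study and within PX-171-010.
- a: days from last initial-study dose to study end.
- G: days from study end to enrollment (the switch, cut at 60).
- b: days from enrollment to first PX-171-010 dose.
- D = a + G + b: days from last initial-study dose to first PX-171-010 dose.
- Protocol 4.1 requires G + b ≤ 90, so at G = 60, b is at most 30.

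**Assumptions for illustration.** Six-dose 28-day cycles in both studies (Days 1, 2, 8, 9, 15, 16). Four cycles in the initial study and six in PX-171-010.

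**Reading 1: within-study exposure = last dose - first dose + 1**
- c cycles span (c - 1) × 28 + 16 days, so E1 = 84 + 16 = 100 and E2 = 140 + 16 = 156.
- Sum rule (G > 60): 100 + 156 = 256.
- Span rule (G ≤ 60): E1 + E2 + (D - 1) = 256 + (D - 1).
- Drop at the cut: D - 1, whatever the number of cycles.

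| a | G | b | D | Span rule | Sum rule | Drop |
|---|---|---|---|---|---|---|
| 0 | 60 | 0 | 60 | 315 | 256 | 59 |
| 0 | 60 | 7 | 67 | 322 | 256 | 66 |
| 0 | 60 | 30 | 90 | 345 | 256 | 89 |
| 30 | 60 | 0 | 90 | 345 | 256 | 89 |
| 30 | 60 | 30 | 120 | 375 | 256 | 119 |

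The rows with a = 30 carry an extra assumption. They apply to the initial study the completion rule that Protocol 3.4 gives for PX-171-010: "An individual subject is considered to have completed the study 30 days after the last administered dose of study drug". The documents do not give the prior studies' own definitions.

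Dose dates need not differ at all. G = 60 with b = 7 gives 322, and G = 61 with b = 6 gives 256. D is 67 in both, and only the enrollment date has moved by a day.

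**Reading 2: within-study exposure runs to the end of each 28-day cycle**
- E1 = 4 × 28 = 112 and E2 = 6 × 28 = 168, so the sum rule gives 280.
- The span rule is fixed by dose dates and is unchanged. At D = 60 it gives 315, so the drop is 315 - 280 = 35 days.
- If only the initial study is counted this way, the sum is 112 + 156 = 268 and the drop is 315 - 268 = 47 days.

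**Effect of the enrollment date.** If the consent date of SAP 5.6 applied here, enrollment would fall in screening (Days -30 to -1, Protocol 7.1), so b would be at least 1. At G = 60, D would then exceed 60, and the span rule could count more than 60 off-drug days.

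**Uninterrupted roll-over.** Ten consecutive cycles span 9 × 28 + 16 = 268 days. With 12 rest days between Day 16 and the next Day 1, D = 13 and the span rule gives 256 + 12 = 268, which is exact. The sum rule under reading 1 gives 256, 12 days short.

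**The case against.** The best defense is that this is a prespecified convention: a short break counts as continuous therapy and a longer one as an interruption. Any cut-off creates a step, and calendar-span exposure already includes planned rest days and dose holds. This holds for a prompt roll-over, where the span rule is exact. It is harder to extend to 60 days. At D = 60 the span rule gives 315 days against 268 for the same ten cycles without a break, an excess of 47 days. The SAP offers no reason for going that far.

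It is also true that most exposure information is reported in other ways, and that each subject's off-drug interval could be recovered from the dosing listing. That limits the damage but does not make the summary table itself interpretable.

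Three stronger readings might be inferred, and the documents do not support them:
- **That the jump is 59 days as a matter of fact.** That figure needs D = 60 and first-to-last-dose exposure within each study, which SAP 7.5 does not state. The other readings above give 35 or 47 days at the same D.
- **That the SAP has no enrollment date at all.** SAP 5.6 uses the consent date for age. What is missing is a statement that it governs the 60-day rule.
- **That adverse event results are distorted.** SAP 7.6.1 bases percentages on subjects who received at least one dose. The optional exposure-based rates in Protocol 10.4.1 name treatment cycles as their example.

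**Conclusion.** The inconsistency is real and confined to one descriptive variable. Combined duration of exposure includes the between-study gap at 60 days or less and excludes it above, so a longer gap can yield a shorter reported exposure. This follows from the SAP wording and the 90-day eligibility limit, without further assumption.

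Its size is conditional. With D = 60 and 4 + 6 six-dose cycles, the drop is 59 days (8.4 weeks) if single-study exposure is first to last dose, and 35 days (5 weeks) if it runs to the end of each cycle. Lags from last dose to study end, or from enrollment to first dose, add to either figure. How far the cohort means, medians or weeks categories move cannot be computed, because the documents do not give the distribution of gaps. AE percentages, cycles, doses, cumulative dose and PX-171-010-only duration are unaffected. The correction is therefore optional.

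**What to change.** Replace the two-branch bullet in SAP 7.5 with one definition for all subjects: (last dose - first dose + 1) in the initial study plus (last dose - first dose + 1) in PX-171-010. Add a summary of the gap from last initial-study dose to first PX-171-010 dose. This removes the step (256 days at both a 60-day and a 61-day gap in the 4 + 6 example), settles the undefined within-study exposure, and makes the enrollment date irrelevant to this variable.

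The cost is one rewritten bullet and one added line. Dosing data for both studies are already to be listed. The downside is that combined exposure becomes shorter for the group at 60 days or less, including an uninterrupted roll-over, which loses its 12 planned rest days (268 to 256 days for 4 + 6 cycles). Rest days and dose holds within a study still count. The separate gap line lets a reader see what has been left out.
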